### Study protocol:

All women admitted to The Center for Recurrent Pregnancy Loss of Western Denmark from January 2016 to March 2020 were identified in this combined case-control and cohort study and screened for study eligibility. Only patients with a history of  $\geq 3$  consecutive spontaneous pregnancy losses were included. Both biochemical (confirmed by a positive human chorionic gonadotropin (hCG) test) and clinical losses (confirmed by an ultrasound examination and/or histology of aspirated tissue from the uterus) documented in hospital records were accepted. Verified extrauterine pregnancy losses, complete molar pregnancies, and induced abortions of social and genetic reasons were not included in the total number of pregnancy losses. Women with significant uterine malformations, significant parental chromosomal abnormalities, irregular and/or abnormal menstrual cycle length (<22 and >35 days interval), <3 consecutive pregnancy losses (n=26), and/or no p-MBL measurement were excluded. 267 women fulfilled all study criteria. The RPL patients were followed until birth of a liveborn child after RPL or until March 2021, whichever came first.

At the first consultation in The Center for Recurrent Pregnancy Loss of Western Denmark, all women underwent a routine diagnostic work-up including collection of an obstetric and gynecologic history, a routine blood analysis with plasma mannose binding lectin (p-MBL)

measurement, a uterine hydrosonegography, hysteroscopy or hysterosalpingography, and in most cases also a parental chromosomal analysis.

According to the individual health profile, the obstetric history, and the results from blood sample, treatment options such as vaginal progesterone, oral prednisolone, intravenous immunoglobulin (IVIG) infusion, and/or subcutaneous heparin were considered. In patients with an estimated good prognosis, only psychological support and close ultrasound scan monitoring (tender loving care) was offered.

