Retrospectively, data was retrieved from the RPL clinical database of The RPL Center in Aalborg University Hospital, Denmark (Data Protection Agency of Region Nordjylland Approval Number 2018-5) in which relevant data is collected on patients from their first consultation and until their contact to the clinic is terminated. Data on perinatal outcomes of all pregnancies before and after RPL was collected at the first consultation, from hospital records, and, when needed, completed by telephone or e-mail correspondence. This included information about mode of conception and delivery, gestational age (GA), birth weight (BW), gender of offspring, volume of peripartum hemorrhage, occurrence of preeclampsia, and perinatal complications. GA was divided into preterm and very preterm birth defined as birth <37 weeks and <32 weeks of gestation, respectively. BW was divided into low and very low BW defined as <2500 g and <1500 g, respectively. Peripartum hemorrhage was divided into moderate hemorrhage of 500-999 ml and severe hemorrhage of  $\geq 1000$  ml lost within 24h after birth including both peripartum hemorrhage during vaginal delivery and caesarean section. Peripartum hemorrhage was routinely estimated and noted by the midwives in the delivery records generally by weighing absorbent bed sheets.

Live births refer to children born alive and who were still alive after 1 week. Miscarriages were divided into early and late miscarriages defined as <12 weeks and 12-21+6 weeks of gestation, respectively. Stillbirth was defined as fetal death  $\geq 22$  weeks of gestation and within 1 week after delivery. pRPL was defined as  $\geq 3$  consecutive pregnancy losses while secondary RPL (sRPL) was defined as  $\geq 3$  consecutive pregnancy losses after the birth of a viable child. Whenever the gender of the fetus was known, it was recorded.

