### *Blood samples*

Routine blood analysis comprised the following plasma and genetic biomarkers: plasma level of MBL, autoantibodies (anti-nuclear antibodies [ANA], anti-ds-DNA-antibodies and anti-thyroid peroxidase [TPO] antibodies, lupus anticoagulant [LAC], anti-cardiolipin antibodies [IgG/IgM ACA] and anti- $\beta 2$ -glycoprotein-I antibodies [IgG/IgM aGPL-I]), thyroid stimulating hormone (TSH), homocysteine, the HLA-DRB1 genotype and hereditary thrombophilic factors (the prothrombin- and factor-V Leiden genetic variants, protein S and C, and antithrombin III).

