#### *Ethical approval*

Since only data on routine investigations and interventions in the RPL Center is analyzed and reported, no approval from the ethics committee was needed.

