### Statistical analysis plan:

#### *Statistical Analysis*

Data was analyzed using Stata/MP 15.0 for Mac, revision 19 June 2017. Level of statistical significance was defined as  $p < 0.05$ . Patients were divided into 3 subgroups according to their p-MBL levels: low ( $\leq 500 \mu\text{g/l}$ ), intermediate ( $501-3000 \mu\text{g/l}$ ), and high p-MBL group ( $>3000 \mu\text{g/l}$ ).

Cross-sectional data on p-MBL levels were compared between RPL patients and the MBL reference group and analysed using  $\chi^2$  test; first comparing prevalence of  $\leq 500 \mu\text{g/l}$  and  $>500 \mu\text{g/l}$  between the two groups and next the same procedure for intermediate and high levels, respectively. The

relative prevalence of low MBL was compared using prevalence proportion ratio (PPR) with 95% confidence intervals (CI).

A binominal logistic regression analysis was performed to identify the possible prognostic value of low and/or high MBL level on the reproductive outcome in first pregnancy after admission which was adjusted for confounding variables known to influence on the reproductive outcome. The reproductive outcome was defined 1= pregnancy loss and 0= pregnancy>12 weeks or birth in the first pregnancy after admission. Patients with no pregnancy after admission, pregnant at the time of admission, and pregnant after admission but <12 weeks of gestation at final follow-up were not included in the logistic regression analysis of reproductive outcome. p-MBL level was defined as 1=p-MBL level  $\leq 500 \mu\text{g/l}$  and 0= p-MBL level  $>500 \mu\text{g/l}$  in the analysis. Confounders included in the analysis were measured at baseline and involved age (continuous), BMI (continuous), number of pregnancy losses before admission (continuous) and exposure to tobacco smoke (1=yes, 0=no). A linear regression analysis was performed to analyze the effect of p-MBL level on birth weight and GA of first birth before and after RPL; all as continuous variables.

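### Does leaving treatment out of the prognostic model make the odds ratio for low p-MBL uninterpretable?

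*Combined protocol and SAP*

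**What the plan says.** The Statistical Analysis section sets the aim of the logistic model as "to identify the possible prognostic value of low and/or high MBL level on the reproductive outcome in first pregnancy after admission". The outcome is loss, against a pregnancy beyond 12 weeks or a birth. Women already pregnant at admission are left out. On adjustment it says: "Confounders included in the analysis were measured at baseline and involved age (continuous), BMI (continuous), number of pregnancy losses before admission (continuous"), with yes/no tobacco exposure as the fourth covariate. No treatment variable appears, and no table or sensitivity analysis by treatment is planned.

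The Study protocol section describes how care was chosen: "According to the individual health profile, the obstetric history, and the results from blood sample, treatment options such as vaginal progesterone", oral prednisolone, intravenous immunoglobulin and heparin were considered. It adds: "In patients with an estimated good prognosis, only psychological support and close ultrasound scan monitoring (tender loving care) was offered". The same section places "a routine blood analysis with plasma mannose binding lectin (p-MBL") in the first-visit work-up. The Blood samples section confirms this ("Routine blood analysis comprised the following plasma and genetic biomarkers: plasma level of MBL") and lists p-MBL beside autoantibodies, TSH, homocysteine, HLA-DRB1 and thrombophilia markers.

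On data, the Study protocol section says that "relevant data is collected on patients from their first consultation and until their contact to the clinic is terminated", and the Ethical approval section says that "only data on routine investigations and interventions in the RPL Center is analyzed and reported". Neither names treatment in the analysed pregnancy as a recorded item.

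**The concern.** Treatment was allocated partly by expected outcome and partly by blood results, and the exposure under study was one of those results. The clinic could know p-MBL before the pregnancy that supplies the outcome. If women with low p-MBL were treated more often, or less often, and treatment alters the risk of loss, the fitted odds ratio mixes the marker with the management that followed it. With no treatment table, a reader could not see whether this happened. The SAP also calls its covariates confounders, which may invite a reader to take the adjusted odds ratio as the effect of MBL itself. What is at stake is interpretation: a real association could be masked, or a null one could look protective or harmful.

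**Working it through.** The documents give no odds ratio, event count or power figure for this model, so there is nothing to reproduce. The check asks how large the mixing could be, then what a treatment-adjusted model would do.

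**Inputs.** All are assumptions except the cohort of 267, which is in the Study protocol section.
- Loss risk in untreated women without low p-MBL: 45%, so odds 0.45/0.55 = 0.818.
- Treatment odds ratio for loss: 0.4 to 0.7.
- True MBL odds ratio: 1.0 or 1.5.
- Treated shares (low p-MBL versus others): 70/40, 40/70, 60/50, 50/60 and 50/50.

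**Formula.** Risk in an MBL group = s × risk(treated) + (1 − s) × risk(untreated), where s is the treated share. The apparent odds ratio is the ratio of the two groups' odds, unadjusted.

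**Worked case.** Take a true MBL odds ratio of 1.0, a treatment odds ratio of 0.4 and shares 70/40.
- Treated odds: 0.818 × 0.4 = 0.327, so risk 0.327/1.327 = 0.247.
- Low p-MBL: 0.7 × 0.247 + 0.3 × 0.45 = 0.308.
- Others: 0.4 × 0.247 + 0.6 × 0.45 = 0.369.
- Odds 0.444 and 0.584, ratio 0.76.

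**Results for treatment odds ratios 0.4 to 0.7:**

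| Treated, low vs others | True 1.0 appears as | True 1.5 appears as |
|---|---|---|
| 70% vs 40% | 0.76 to 0.90 | 1.12 to 1.34 |
| 40% vs 70% | 1.11 to 1.31 | 1.66 to 1.94 |
| 60% vs 50% | 0.91 to 0.97 | 1.34 to 1.44 |
| 50% vs 60% | 1.04 to 1.10 | 1.55 to 1.61 |
| 50% vs 50% | 1.00 | 1.47 to 1.50 |

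Baseline risks of 30% or 60% move these by about 0.01 at most. If treatment has no effect, nothing is distorted. If treated women have twice the odds of loss, for example because they were the poorer-prognosis cases, shares of 60/40 give 1.15 for a true 1.0. The direction is therefore open as well.

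**Scale against sampling error.** Suppose 60% to 80% of the 267 women enter the model (160 to 214), 20% have low p-MBL and 40% have a loss. With 160 women the four expected cells are 12.8, 19.2, 51.2 and 76.8. The standard error of the log odds ratio is √(1/12.8 + 1/19.2 + 1/51.2 + 1/76.8) = 0.403. The 95% interval around a true 1.0 is exp(±1.96 × 0.403), or 0.45 to 2.21. With 214 women it is 0.50 to 1.98. The 30-point scenarios for a true 1.0 lie well inside both intervals.

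**What adjusting for treatment would do.** Let MBL and treatment both be truly without effect, with 45% loss and 20% low p-MBL. Let 10%, 20% or 30% of losses in women planned for treatment occur before it starts, so that they are coded untreated. A model adjusted for treatment received then gives an MBL odds ratio of 1.06, 1.12 or 1.17 with planned shares 70/40, and 0.92, 0.86 or 0.80 with 40/70. Coding by planned treatment gives 1.00 throughout, but no section says that a plan documented before the outcome was recorded.

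**The case for a change.** The strongest case for a change is that p-MBL need not have steered treatment directly. Any association between MBL and the factors that did steer it is enough, and the Study protocol section says that blood results and expected prognosis were among them. A table of treatment by MBL group would be cheap and would settle whether the groups were managed alike. The routine-care statement under Ethical approval justifies the absence of ethics review; it does not define what the odds ratio means.

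Much of this stands. The omission is real, the meaning of the odds ratio has to be inferred, and the figures above reach material size if the treatment gap is wide. But the argument shows a possibility, not a distortion. It needs two conditions, a difference in treatment by MBL group and an effect of treatment on loss, and the documents establish neither.

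The stronger remedies give no demonstrated gain. Treatment may lie on the path from the p-MBL result to the outcome, and it was also chosen on other prognostic grounds, so conditioning on it changes the question and can add bias. Restricting to supportive care selects women judged to have a good prognosis and shrinks the sample. A single treated/untreated variable pools four different therapies. Adding primary versus secondary recurrent loss as a covariate does not address treatment, and nothing in the documents shows what it would gain.

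**Conclusion.** No change to the plan is needed. A model built from baseline covariates is a sound choice for the prognostic value of a marker measured at first consultation, and following the SAP as written gives a valid estimate of prognosis under this clinic's usual care. That is also the natural reading of a retrospective study of routine practice. The estimate would not support a claim about MBL independent of treatment, but the documents make no such claim.

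The possible distortion ranges from none to a null odds ratio appearing as 0.76 to 1.31, for treated shares differing by up to 30 points and treatment odds ratios of 0.4 to 0.7. Every one of those inputs is assumed. The figures are unadjusted, and adjustment for number of losses may remove part of the effect. Whether treatment differed by MBL group cannot be told from the documents.

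What remains is reporting detail that analysts can supply sensibly at write-up: describing the odds ratio as prognosis under usual care and, if treatment in the analysed pregnancy was recorded, showing it by MBL group. Neither alters the analysis.

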According to perinatal data on first birth before and after admission, the differences in categorical data were determined by  $\chi^2$  test, but in comparisons in which less than 5 numbers were expected the Fisher's exact test was performed. Differences in continuous variables were determined by the two-sample Mann-Whitney U test if data was non-normally distributed, and by t-test if data fitted a normal distribution. When analyzing the previous children's sex, only women with one or more children of same sex born before the RPL diagnosis with a GA >22 weeks were included. Women with sRPL with  $\geq 2$  children of mixed gender were excluded from analyses involving sex of child(ren) born before admission. Sex ratio was reported as a male:female ratio.

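### The male:female ratio of children born before RPL is taken only from women whose children are all of one sex, which selects on the outcome and can push a ratio other than 1 further from 1

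*Combined protocol and SAP*

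**What the plan says.** The rule is in the last part of the Statistical Analysis section. For previous children's sex, "only women with one or more children of same sex born before the RPL diagnosis with a GA >22 weeks were included". The next sentence repeats this as an exclusion: women with secondary RPL and two or more "children of mixed gender were excluded from analyses involving sex of child(ren) born before admission". The section ends: "Sex ratio was reported as a male:female ratio".

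The same paragraph sets its perinatal comparisons in terms of one birth per woman: "According to perinatal data on first birth before and after admission". It does not say whether the sex ratio follows that convention, or whether it counts women or children. It gives no reason for the exclusion and plans no analysis that keeps the excluded women.

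The Study protocol section states that "267 women fulfilled all study criteria" and defines secondary RPL as at least three "consecutive pregnancy losses after the birth of a viable child". It does not say how many women had an earlier birth, how many children each had, or how many fall under the exclusion. On the availability of sex data it says: "Whenever the gender of the fetus was known, it was recorded".

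**The concern.** A woman with one earlier child always enters the analysis. A woman with two or more enters only if their sexes agree, and sex is what the ratio measures. The retained sample is therefore enriched for all-boy and all-girl families. Whichever sex is the more common is over-represented, and more so as families get larger.

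The reported figure is then not the sex ratio of children born before RPL. It mixes that ratio with the distribution of family size, and a reader cannot separate the two because neither the family sizes nor the number excluded is stated. An excess of boys or girls would look larger than it is, and women would be lost from what is already only part of a cohort of 267.

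**Working it through.** **Inputs from the documents.** The inclusion and exclusion rule and the reported measure (Statistical Analysis); the total of 267 women (Study protocol). The plan gives no sex ratio, excluded count or family-size distribution, so there is no figure of its own to reproduce.

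**Assumptions.** Births are independent with P(boy) = p, q = 1 − p and true ratio r = p/q. Among women with an earlier birth, shares s1, s2 and s3 have one, two and three earlier children. I take s2 from 10% to 40% and s3 from 0 to 10%. True ratios of 1.00, 1.05, 1.3 and 1.5 are illustrations.

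**Step 1: families of a given size.** All-boy and all-girl families of k children have probabilities p^k and q^k, so their ratio is r^k. For two-child families, 1.05 becomes 1.05² = 1.10, 1.3 becomes 1.69 and 1.5 becomes 2.25. One-child families dilute this.

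**Step 2: all retained women.**

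- Share dropped = s2·2pq + s3·(1 − p³ − q³)
- Per-woman ratio = (s1·p + s2·p² + s3·p³) / (s1·q + s2·q² + s3·q³)
- Per-child ratio: the same, with the s2 terms multiplied by 2 and the s3 terms by 3

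Worked example, r = 1.5 (p = 0.6, q = 0.4):

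- s2 = 0.2, s3 = 0: boys 0.8×0.6 + 0.2×0.36 = 0.552; girls 0.8×0.4 + 0.2×0.16 = 0.352; ratio 1.568; dropped 0.2×0.48 = 9.6%.
- s2 = 0.4, s3 = 0.1: boys 0.3 + 0.144 + 0.0216 = 0.4656; girls 0.2 + 0.064 + 0.0064 = 0.2704; ratio 1.722; dropped 1 − 0.4656 − 0.2704 = 26.4%.

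| True ratio | s2, s3 | Dropped | Per woman | Per child |
|---|---|---|---|---|
| 1.00 | 0.2, 0 | 10.0% | 1.00 | 1.00 |
| 1.00 | 0.4, 0.1 | 27.5% | 1.00 | 1.00 |
| 1.05 | 0.1, 0 | 5.0% | 1.053 | 1.055 |
| 1.05 | 0.2, 0 | 10.0% | 1.056 | 1.060 |
| 1.05 | 0.4, 0.1 | 27.5% | 1.068 | 1.079 |
| 1.3 | 0.2, 0 | 9.8% | 1.338 | 1.370 |
| 1.3 | 0.4, 0.1 | 27.0% | 1.422 | 1.506 |
| 1.5 | 0.1, 0 | 4.8% | 1.532 | 1.561 |
| 1.5 | 0.2, 0 | 9.6% | 1.568 | 1.625 |
| 1.5 | 0.4, 0.1 | 26.4% | 1.722 | 1.880 |

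**Step 3: does the direction need independence?** Not for a ratio that counts children, in families of at most two. Let retained families contain M boys and F girls, and let m mixed families be dropped. Each mixed family has one boy and one girl, so the full ratio is (M + m)/(F + m) and the reported ratio is M/F. Since M(F + m) − F(M + m) = m(M − F), the reported ratio is further from 1 whenever M ≠ F.

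**Step 4: where the effect vanishes.** Suppose the target is the sex of the first birth, and a first-born boy multiplies the chance of entering the cohort by 1.5 while later children's sex has no influence. In two-child women with births otherwise 50:50, the retained ratio is 1.5 and so is the first-birth ratio. If the underlying birth ratio is 1.05, the retained ratio is 1.5×1.05² = 1.65 against a first-birth ratio of 1.5×1.05 = 1.58.

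**The case against.** The strongest reply is that the SAP's scope is wider than a sex ratio. Its exclusion covers every analysis involving the sex of earlier children, which may include comparing mothers of boys only with mothers of girls only. For that contrast a woman with both sexes has no clear category, and restriction is a recognised choice. This stands: the same-sex-only analysis need not be abandoned. It does not justify using the restricted sample as the denominator for a sex ratio, which is the only summary the section names.

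A second reply is that the effect may be minor. Near the ratio of 1.05 the shift is 0.01 to 0.03. Even if all 267 women contributed, which is an upper bound, the standard error of the log ratio near 1 would be about 2/√267 = 0.12, a 95% interval of roughly a factor of 1.27 either way. At a true 1.2 the largest assumed family sizes give 1.28, a factor of about 1.07. So the bias is small beside sampling error unless the true ratio is well away from 1, and no such ratio is documented. This stands as a limit on size. It does not remove the bias, which would not shrink with more women.

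Third, first-child sex answers a somewhat different question. If risk depended only on the last child, the first-birth ratio would miss it: under 50:50 births it would be 1.0 in two-child women. That is a reason to keep both analyses. The rule is also openly declared, so the complaint is about what the ratio means, not about concealment.

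A reader might go further and infer that the rule creates a departure from 1:1 where none exists, or a false difference between p-MBL groups. The documents support neither. At a true ratio of 1 the rule leaves the ratio at 1. A spurious group difference would need a true ratio other than 1 and family sizes that differ by p-MBL level, and nothing in the documents indicates the latter.

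**Conclusion.** The point holds in a limited form. The reported ratio comes from a sample selected on the outcome. With independent births, or for a child-level count in families of at most two, a true ratio other than 1 is pushed away from 1. Under the assumed family sizes (20% with two children, up to 40% with two plus 10% with three), 1.05 becomes about 1.06–1.07 per woman and up to 1.08 per child, and 1.5 becomes 1.57–1.72 per woman. The matching loss is roughly 10–27% of women with a prior birth. That range follows from the assumptions and cannot be read from the documents; 10% of women with two children would give about 5%.

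Nor does the rule exaggerate every departure. A first-birth ratio is affected little or not at all if risk depends only on the first child's sex. Because the SAP does not name the unit of its ratio, a reader cannot tell which case applies. The change is worth making because it is cheap, not because the bias is shown to be large.

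**What to change.** Add to the Statistical Analysis section, in substance: the male:female ratio before RPL is computed from each woman's first birth before RPL with GA above 22 weeks and known sex, one child per woman, in all women with such a birth, including those whose children are of both sexes. Define first as the earliest such birth. State the unit of the ratio, and report the number of women with mixed-sex children and the distribution of earlier children per woman. Keep the same-sex-only analysis, labelled as a secondary or sensitivity analysis contrasting boys-only with girls-only mothers.

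The cost is a few sentences of wording and one re-tabulation. Offspring sex is already among the data collected for pregnancies before and after RPL, and the SAP already uses the first birth for its other perinatal comparisons. The downside is that mothers of both sexes are classified by their first child only; the retained secondary analysis partly covers this.
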